6.13.6. Electrocardiograms

Electrocardiogram (ECG) assessment of normality and clinical significance will be listed by treatment group. Myocardial information and quantitative results including PR, QRS, QTcB (Bazett's correction), QTcF (Fridericia's correction) and RR intervals will be provided in patient listings. In addition, listings and summaries of outlying corrected QT intervals (QTc, QTcB and QTcF) will be provided for each scheduled time point.

Baseline ECGs are ECGs performed either during screening or predose during the study. Changes in QT from baseline, delta QT, will be calculated by subtracting the respective reading taken at the same nominal time during screening from the reading taken after LY2157299 dosing on specified days as per protocol schedule. Similarly, changes in RR from baseline (ie. delta RR) will be calculated. Delta QT will then be analyzed using a linear mixed-effects model with treatment arm, timepoint and delta RR as fixed effects, treatment-by-time interaction and patient as a random effect (Dmitrienko and Smith 2003). Least square means by timepoint and treatment arm together with 90% confidence intervals will be provided. Mean differences and 90% confidence intervals between treatment arms will be estimated from the model.

If data warrant, additional exploratory analyses may be conducted using appropriate modeling techniques.

The ECG chemistry laboratory values will be listed and summarized separately from other laboratory values.

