Formal assessment of time-linear kinetics, that is, whether $\text{AUC}(0-\infty)$, Day 1 and $\text{AUC}(0-\infty)$, Day 14 are similar, was not possible, due to the limited PK sampling on Day 1. However, no accumulation of LY2157299 in the 5 cohorts was observed over the 14-day BID dosing regimen, as shown by the accumulation ratio (observed to be approximately 1). Additionally, the $\text{C}_{\text{max,ss}}$ on Day 1 and Day 14 in the same patient also appeared to be similar.

A population PK model, based on Cohort 1 through 5 data, was developed. A first order absorption linear 2-compartment model, with elimination from the central compartment provided the best fit to the plasma data. The mean population clearance of LY2157299 was CCI L/h with standard error, expressed as a percent coefficient of variation of CCI % and the steady state volume of distribution (V_{ss}) was CCI L. From the population PK analysis of all 5 cohort data, the between-patient variance was estimated to be CCI % on the population apparent clearance (CL/F). The between-occasion variability on CL/F was estimated at CCI %.

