5.6.5.2. Combination of LY2157299 Monohydrate with Lomustine

In Part B of Study JBAH, LY2157299 was administered for 1 week and lomustine was co-administered on Day 7. Following BID multiple dosing for 6 days, LY2157299 would have achieved steady state distribution in patients due to its relatively short half-life. Hence, comparison of LY2157299 PK profiles on Day 6 against Day 7 (in presence of lomustine) will allow detection of any potential alterations in absorption and disposition. Pharmacokinetic profiles of LY2157299 following administration of CCI mg BID (Cohort 1) and CCI mg BID (Cohort 2) on Days 6 and 7 were similar. Hence, co-administration of lomustine did not appear to alter the LY2157299 PK profile.

Specifically, following administration of 80 mg BID, mean $\text{C}_{\text{max,ss}}$ of CCI and CCI $\mu\text{g}/\text{L}$ and exposures (area under the concentration versus time curve during 1 dosing interval [$\text{AUC}(0-\tau)$]) of CCI and CCI $\mu\text{g} \cdot \text{h}/\text{L}$, respectively were achieved. For Cohort 2, mean $\text{C}_{\text{max,ss}}$ of CCI and CCI $\mu\text{g}/\text{L}$ and exposures ($\text{AUC}_{0-\tau}$) of CCI and CCI $\mu\text{g} \cdot \text{h}/\text{L}$, respectively were achieved.

As expected, there was an increase in observed exposure with dose increase between the 2 cohorts. The variability estimates (percent coefficient of variation [CV%]) of PK parameters appear to be slightly higher in the presence of lomustine when compared with LY2157299 alone

(Days 6 and 7) and then again reduced on Day 12±2. This could be an artifact of the relatively small sample size in Study JBAH, Part B (n=13 Cohort 1 and n=8 Cohort 2) or a valid observation, and will be revisited during the planned first safety interim analysis of Study H9H-MC-JBAL (JBAL).

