9.1. Treatments Administered

The following treatments will be administered in this study:

- LY2157299 Monotherapy:
 - LY2157299 300 mg/day, given orally as three 50-mg tablets BID for 14 days, followed by 14 days of rest, equaling a 28-day cycle.
- LY2157299 plus lomustine therapy:
 - The first lomustine dose will be given as 100 mg/m².
 - Remaining doses (starting with the second lomustine dose) are based on the investigator's discretion and will be given orally once every 6 weeks at 100 to 130 mg/m².
 - LY2157299 300 mg/day, given orally as three 50-mg tablets BID for 14 days, followed by 14 days of rest, equaling a 28-day cycle.
- Lomustine plus placebo therapy:
 - The first lomustine dose will be given as 100 mg/m².
 - Remaining doses (starting with the second lomustine dose) from 100 to 130 mg/m² are based on the investigator's discretion and will be given orally once every 6 weeks..
 - LY2157299 -matched placebo, given orally as 3 tablets BID for 14 days, followed by 14 days of rest, equaling a 28-day cycle.

Lomustine doses should be rounded to the lowest available capsule strength.

Weight is used to determine dose and should be assessed at each cycle, and dose should be recalculated for each cycle.

The investigator or his/her designee is responsible for the following:

- explaining the correct use of the drug(s) and planned duration of each individual's treatment to the patient/site personnel,
- verifying that instructions are followed properly,
- maintaining accurate records of study drug dispensing and collection,
- and returning all unused medication to Lilly or its designee at the end of the study.

Note: In some cases, sites may destroy the material if, during the investigator site selection, the evaluator has verified and documented that the site has appropriate facilities and written procedures to dispose clinical trial materials.

Patients will be instructed to contact the investigator as soon as possible if they have a complaint or problem with the study drug so that the situation can be assessed.

To be considered compliant, the minimum planned treatment of LY2157299 is 10 days and a maximum of 14 days per 28-day cycle and at least cc1% of the allocated LY2157299 prescribed dose has to be administered within each cycle.

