10.3.2. Other Safety Measures

10.3.2.1. Collection of Electrocardiograms

For each patient, 12-lead digital ECGs will be collected according to the Study Schedule ([Attachment 1](#)) as single ECGs for overread. Patients must be supine for approximately 5 to 10 minutes before ECG collection and remain supine but awake during ECG collection.

Electrocardiograms may be obtained at additional times, when deemed clinically necessary. Collection of more ECGs than expected at a particular time point is allowed when needed to ensure high quality records.

Electrocardiograms will be interpreted by a qualified physician (the investigator or qualified designee) at the site as soon after the time of ECG collection as possible, and ideally while the patient is still present, to determine whether the patient meets entry criteria and for immediate patient management, should any clinically relevant findings be identified.

After enrollment, if a clinically significant increase in the QT/QTc interval from baseline, or other clinically significant quantitative or qualitative change from baseline, is present, the investigator will assess the patient for symptoms (for example, palpitations, near syncope, syncope) and to determine if the patient can continue in the study. The investigator or qualified designee is responsible for determining if any change in patient management is needed and must document his/her review of the ECG printed at the time of evaluation.

All digital ECGs will be electronically transmitted to a designated central ECG laboratory. A cardiologist at the central ECG laboratory will then conduct a full overread on the ECG (including all intervals); a report based on data from this analysis will be issued to the investigative site. All data from the overreads will be placed in the Lilly database for analytical and study report purposes.

When there are differences in ECG interpretation between the investigator (or qualified designee) and the cardiologist at the central ECG laboratory, the investigator (or qualified designee's) interpretation will be used for study entry and immediate patient management. Interpretations from the cardiologist at the central ECG laboratory will be used for data analysis and report writing purposes.

The investigator (or qualified designee) must document his/her review of the ECG printed at the time of evaluation, the final overread ECG report issued by the central ECG laboratory, and any alert reports.

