Attachment 3. Pharmacokinetic Sampling

In conjunction with the Study Schedule of Events, the following PK draws will be conducted.

Sparse PK Sampling Schedule for Phase 2

Sample Number	Cycle	Day	Sampling Windows for plasma PK	ECG and ECG Chemistry	Optional CSF collection ^b
1	1	1	Predose ^a	X	
2	1	1	0.5 to 2 hours		0.5 hours ^b
3	1	1	3.5 to 5 hours	X	4 hours
4	1	3	Predose ^a	X	Predose
5	1	14	Predose ^a	X	Predose
6	1	14	0.5 to 2 hours		0.5 hours
7	1	14	3.5 to 5 hours	X	4 hours
8	1	15	Morning	X	Morning
9	1	16	Morning		

Abbreviations: CSF = cerebrospinal fluid; ECG = electrocardiogram; PK = pharmacokinetic.

^a The predose sample has to be taken before receiving any LY2157299 monohydrate.

^b CSF collection time as close as possible to plasma sample.

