Study day	If assessment is on or after date of first LY2157299/ LY2152799-matched placebo dose then (date of assessment) – (date of first study treatment dose) + 1 If assessment precedes first treatment dose then (date of assessment) – (date of first study treatment dose)

	There is no study day 0. Study day 1 is the date of first dose and study day -1 is the day before the first dose.
Cycle day	If assessment is on or after date of first LY2157299/ LY2152799-matched placebo dose then (date of assessment) – (date of first study treatment dose in cycle) + 1 If assessment precedes first treatment dose then (date of assessment) – (date of first study treatment dose in cycle) There is no cycle day 0. Cycle day 1 is the date of first dose in the cycle and cycle day -1 is the day before the first dose.
Baseline	For change from baseline analysis, baseline value is defined as the last reported measure on or before the first dose date (or discontinuation, if no treatment is given). For change from baseline within a cycle, the measure prior to the first dose if that cycle is baseline.
Study treatment period	Time from treatment start to discontinuation from study treatment
Post-discontinuation – short-term follow-up	The short term follow-up period begins 1 day after discontinuation of study treatment and lasts approximately 30 days (Visit 801).
Post-discontinuation – long-term follow-up	The long-term follow-up period begins 1 day after the short-term follow-up period (Visit 801) is completed and continues until death to collect survival data.

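### The QT analysis has three inconsistent baseline rules, one of which literally admits on-drug ECGs; the SAP should name a single drug-free baseline

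*SAP*

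**What the plan says.** Two consecutive sentences in SAP 6.13.6, matched in Protocol 12.2.10.1, set the ECG baseline. The first is general: "Baseline ECGs are ECGs performed either during screening or predose during the study". The second defines delta QT as "subtracting the respective reading taken at the same nominal time during screening from the reading taken after LY2157299 dosing", and delta RR is built the same way.

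A third rule stands in SAP 6.1, Table JBAL.6.1. For change from baseline, the "baseline value is defined as the last reported measure on or before the first dose date". The same table adds that, for change within a cycle, baseline is the measure before that cycle's first dose.

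Delta QT goes into a linear mixed model with arm, time point, delta RR and arm-by-time interaction, and patient as a random effect. Baseline QT is not among the terms. The output is least-squares means by arm and time point, and between-arm differences, each with 90% intervals.

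On collection, Protocol 10.3.2.1 says ECGs are taken "as single ECGs for overread". Attachment 1 has one prestudy mark in the ECG row, without a clock time. Attachment 3, which opens with "In conjunction with the Study Schedule of Events, the following PK draws will be conducted", is the only visible table that gives ECG times.

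**The concern.** A change-from-baseline analysis needs one stated reference value per patient and time point. Here an analyst meets three candidates: a time-matched screening reading, any predose reading, and the last value up to the first dose date. The first has no visible data behind it. The second, taken literally, includes ECGs recorded while the patient is on drug.

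The drug is "given orally as three 50-mg tablets BID for 14 days, followed by 14 days of rest", so a predose ECG on Day 3 or Day 14 follows several doses. Subtracting such a reading from a later one on the same drug removes whatever effect persists at trough. That error runs toward finding no QT effect, which is the wrong direction for a safety analysis.

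Delta QT is the only modelled QT analysis described, and delta RR enters it as a covariate. An unclear baseline therefore affects both the outcome and an adjustment term.

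**Working it through.** The plan states no power, error rate or expected effect for the QT analysis, so there is no figure to reproduce. The check is a count of readings followed by a bound on the possible attenuation.

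**Step 1. Count the timed ECGs (Protocol Attachment 3).**

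| Cycle 1 reading | After first dose? | Predose? | Visible time-matched screening ECG? |
|---|---|---|---|
| Day 1 predose | no | yes | not applicable |
| Day 1, 3.5-5 h | yes | no | none |
| Day 3 predose | yes | yes | none |
| Day 14 predose | yes | yes | none |
| Day 14, 3.5-5 h | yes | no | none |
| Day 15 morning | yes | no | none |

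There are 6 timed ECGs, of which 5 follow the first dose. Of the 3 predose readings, 2 (Days 3 and 14) are on drug. Attachment 1 also marks an ECG on Day 26, with no visible time.

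**Step 2. Set the rules against these readings.**

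- Delta QT sentence: screening only, time-matched. No on-drug ECG enters, but no matched reading is visible.
- Baseline sentence: screening or predose. It admits Day 1 predose, and also Days 3 and 14.
- Table JBAL.6.1: last value up to the first dose date. It excludes Days 3 and 14. It works by date, so it does not by itself separate the Day 1 predose ECG from the 3.5-5 h ECG on the same date.

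**Step 3. Bound the loss if an on-drug predose ECG became the baseline.** Assume a QT effect proportional to concentration, a one-compartment decline, 12-hour dosing, and k = ln 2 / half-life. For a reading t hours after a dose:

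- share of effect lost = exp(-k(12 - t)), with t from 3.5 to 5 h
- accumulation ratio = 1 / (1 - exp(-12k))

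The half-life figures are redacted, so the values below are assumptions.

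| Assumed half-life | Accumulation ratio | Share lost, t = 3.5 to 5 h |
|---|---|---|
| 2 h | 1.02 | 5-9% |
| 3 h | 1.07 | 14-20% |
| 4 h | 1.14 | 23-30% |
| 8 h | 1.55 | 48-55% |
| 12 h | 2.00 | 61-67% |

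For example, at 4 h, k = 0.173 and exp(-0.173 × 8.5) = 0.23. Protocol 5.6.5.1 reports that "no accumulation of LY2157299 in the 5 cohorts was observed over the 14-day BID dosing regimen", with a ratio of about 1, and 5.6.5.2 says "LY2157299 would have achieved steady state distribution in patients due to its relatively short half-life". Both point to the upper rows, that is, roughly 5-30%.

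**Step 4. Check the remedy by an illustrative simulation.** Assumptions: 20,000 patients per arm, true effect 10 ms, time-of-day shift 5 ms in both arms, and trough effect 25% of the post-dose effect.

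| Baseline used | Active change | Placebo change | Difference |
|---|---|---|---|
| Screening | 15.0 ms | 5.0 ms | 10.1 ms |
| Day 1 predose | 15.0 ms | 5.0 ms | 10.0 ms |
| Day 14 predose | 12.4 ms | 4.9 ms | 7.5 ms |

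Either drug-free baseline recovers the between-arm effect. The on-drug baseline loses the assumed quarter. With either drug-free baseline, the within-arm changes still carry the 5 ms time-of-day shift.

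**The case against.** A reader might infer that timed screening ECGs are not collected and that the delta QT analysis therefore cannot be run. The documents do not support this. Marks in Attachment 1 are per day: Days 1 and 14 carry one mark each, yet Attachment 3 lists two ECGs on each. Collecting single ECGs may simply mean no replicates, and Protocol 10.3.2.1 allows extra recordings. The Comments column, where times could be given, is redacted. Attachment 3 is a PK-linked table, so its lack of a screening row proves little. In any case, drug-free readings exist at screening and at Day 1 predose, so a change from baseline can be computed.

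A reader might also infer that the plan biases the QT effect to zero. It does not. The delta QT sentence names only screening readings, and neither rule in Table JBAL.6.1 reaches Days 3 or 14. On-drug baselines enter only if an analyst falls back on the looser sentence, and the loss is then partial.

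The stakes are also limited. Summaries of outlying QTc values and the central overread do not depend on delta QT, and no visible decision rule does. The Grade 3 QTc prolongation in the earlier combination study (Protocol 5.6.4.2) was isolated, not considered related to study therapy and not considered serious. Protocol 5.6.3 reports no substantive nonclinical QT risk up to a stated, redacted concentration.

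All of this stands. It narrows the point but does not reconcile the three rules.

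**Conclusion.** The QT baseline is inconsistently specified and should be settled in the SAP. Time-matched screening readings are not visible for any of the five timed Cycle 1 ECGs after the first dose, and one stated rule literally permits two on-drug predose ECGs as baselines. If one of these were used for a 3.5-5 h reading, the estimated effect would shrink by about 5-30%. That range assumes a concentration-proportional effect, one-compartment decline and a half-life of 2 to 4 hours, chosen because reported accumulation is near 1; a longer half-life would raise it. As the delta QT formula is written, this attenuation is a risk of the fallback choice and not a consequence of the plan.

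**What to change.** In SAP 6.13.6, and in Protocol 12.2.10.1 when it is next revised:

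- Define baseline QT and RR, for all later time points, as the Cycle 1 Day 1 predose ECG, or the screening ECG if that is missing. This follows the intent of Table JBAL.6.1; saying predose explicitly keeps out the Day 1 post-dose ECG.
- Remove the same-nominal-time screening clause unless timed screening ECGs are in fact collected. If they are, state their times.
- State that Day 3 and Day 14 predose ECGs are not baselines.
- Add baseline QT as a covariate in the mixed model.

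Averaging screening with Day 1 predose is not advised: it departs from the last-value rule and mixes one-ECG and two-ECG baselines across patients.

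The cost is wording and one model term, because the Day 1 predose ECG is already scheduled. Both documents allow a change to a non-principal analysis method to be made and justified in the SAP without a protocol amendment. The drawback is that correction for time of day then comes from the concurrent lomustine plus placebo arm, through the between-arm differences already planned. Within-arm changes remain confounded with time of day and should be reported with that caveat.

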12.2.10.1. Cardiac Safety Analyses

Refer to [Attachment 1](#) and [Attachment 2](#) for timing of ECGs, ECG chemistry, and ECHOs.

Echocardiography/Doppler assessments will be done as outlined in [Attachment 6](#).

Baseline ECGs are ECGs performed either during screening or predose during the study. Changes in QT from baseline, delta QT, will be calculated by subtracting the respective reading taken at the same nominal time during screening from the reading taken after LY2157299 dosing on specified days in [Attachment 1](#). Similarly, changes in RR from baseline, delta RR, will be calculated. Delta QT will then be analyzed using a linear mixed-effects model (Dmitrienko and Smith 2003).

In addition, listings and summaries of outlying corrected QT intervals (QTc [QTc – Bazett's correction (QTcB) and QTc – Fridericia's correction (QTcF)]) will be provided for each scheduled time point.

If data warrant, additional exploratory analyses may be conducted using appropriate modeling techniques.

The ECG chemistry laboratory values will be listed and summarized separately from other laboratory values.

Individual patient listings and summaries by treatment arm will be provided for all echocardiograph variables. Shift tables indicating maximum changes from baseline will be provided for qualitative variables and absolute and/or percent change from baseline for quantitative variables.

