5.2. Determination of Sample Size

CCI patients will be entered with the aim of randomizing **CCI** patients to 1 of 3 treatment arms in this multicenter study. The randomization will be in **CCI** patients in LY2157299 monotherapy, **CCI** patients in LY2157299 plus lomustine therapy, and **CCI** patients in lomustine plus placebo therapy).

The primary objective is to compare the OS distributions between the combination arm, LY2157299 plus lomustine therapy with the control arm, lomustine plus placebo using a Bayesian augmented control design. By incorporating historical information regarding the control arm (ie, lomustine plus placebo) into the Bayesian model, it is possible to improve the operating characteristics compared to a standard (frequentist) analysis using log rank test with the assumptions that the HR = **CCI**, Power = **cci**%, Type I error = 0.1 (one-sided).

At the final analysis, the combination arm will be considered superior to the control arm if after **CCI** patients have completed at least 2 years of follow-up, the posterior probability is greater than **cci**% that the HR for OS of the combination arm versus control arm is <1 (ie. $\text{Pr}(\text{Treatment HR} < 1) > \text{cci}\%$).

This study is designed to observe approximately **CCI** events at the final analysis and approximately **CCI** events at the **CCI** interim analysis. 5000 Simulations (FACTS v2.4) assuming the following were carried out:

- Exponential survival model using summary hazard rates from 2 previous lomustine trials (Study H6Q-MC-JCBF [data on file and Wick et al. 2010a], Batchelor et al. 2010a;) along with data from the lomustine plus placebo arm in this study.
 - The average median OS time is 8.5 months giving an average control hazard rate across these 2 studies of **CCI** /week
 - The fixed prior distribution for the control hazard rate has a Gamma distribution with a mean of **CCI** and a weight of 1 (weak prior) or a weight of 10 (strong prior)
- The prior distribution of the log HR between the combination arm and lomustine plus placebo is assumed to be Normally distributed with a mean of zero and a standard deviation of 100 (weak prior)
- ‘True’ hazard ratios (HR) of **CCI** (success), **cci** (null) and **CCI** (failed) and **cci** (extreme fail) arm observed at interim analysis
- Patients are randomized in a **CCI** ratio (favoring the LY2157299 plus lomustine arm)
- Enrollment rate is **cci** patients/month (**CCI** patients/week)

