5.3. Method of Assignment to Treatment

Patients who meet all criteria for enrollment will be randomly assigned in a $1:1:1$ ratio to receive treatment on LY2157299 monotherapy, LY2157299 plus lomustine therapy, or lomustine plus placebo therapy using an interactive voice-response system (IVRS). This will occur before Cycle 1 Day 1. There is no plan to have an unblinded site representative for this study.

A dynamic allocation method, introduced by Pocock and Simon (1975) (and extended for unequal treatment group sizes by Han et al. [2009]), will be adopted to minimize imbalance between treatment arms according to the following factors:

- baseline ECOG PS (0, 1)
- age (≤ 60 , > 60 years)

- GB, primary or secondary at study entry

The randomization parameter P will be set at 0.9 to maximize the benefit of the allocation procedure, while keeping treatment assignments unpredictable. Randomization will be monitored periodically and the randomization parameter will be modified if necessary.

6. A Priori Statistical Methods

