6.11.2.2. MDASI-BT Analyses

The rate of compliance with completing MDASI-BT will be summarized at the group-level at each assessment: prestudy (baseline), end of cycle 1 and thereafter every 2 cycles (26 ± 2 days) starting at cycle 2 and at discontinuation (Visit 801). Compliance is defined as the number of completed questionnaire/number of expected questionnaire to be completed at the time of the study.

For those patients who had completed at least one assessment, descriptive statistics will be provided for the core symptoms, brain tumor symptoms, symptom interference, and symptom groupings (affect, cognition, focal neurologic deficit, treatment-related symptoms, generalized/disease status symptoms, and gastrointestinal symptoms) at each assessment period by treatment arms. This summary will include number of patients in each arm, number of patients with completed questionnaire, mean, standard deviation, median, minimum, maximum scores and change from baseline.

For those patients who completed a baseline and one post-baseline questionnaire, change from baseline on core symptoms, brain tumor symptoms, symptom interference, and symptom groupings will be assessed. Repeated measures ANOVA will be performed to assess the mean differences in change from baseline between treatment arms, adjusting for baseline score if needed. Least squares mean, mean differences, including 95% confidence interval and p-values indicating significant differences between treatment arms will be provided. Plots of mean and standard deviation for core symptoms, brain tumor symptoms, symptom interference, and symptom groupings over time and change from baseline plots will be provided.

The minimally important difference (MID) is used to assess and interpret mean score differences between treatment arms. A minimally important difference of 1.2 (as defined in the MDASI user manual) will be used as a reference in the time to worsening analysis. Data from each treatment

arm will be analyzed using Kaplan-Meier plots with censoring at the last assessment for patients with no worsening. Median time to worsening with 95% confidence interval will be provided. The proportion of patients who experienced a change from baseline score of 1.2 will also be summarized for each treatment arm and compared between treatment arms.

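### The delta QT model leaves out baseline QT and RR, so the between-arm 90% CIs are somewhat wider than they need be and carry part of any chance baseline imbalance

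*SAP*

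**What the plan says.** SAP 6.13.6 defines the response as a change score: "Changes in QT from baseline, delta QT, will be calculated by subtracting the respective reading taken at the same nominal time during screening" from the post-dose reading. Delta RR is formed in the same way. The model is then listed: "Delta QT will then be analyzed using a linear mixed-effects model with treatment arm, timepoint and delta RR as fixed effects", together with "treatment-by-time interaction and patient as a random effect". Its output includes the comparison between arms: "Mean differences and 90% confidence intervals between treatment arms will be estimated from the model".

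Protocol 12.2.10.1 is less specific. It says only "Delta QT will then be analyzed using a linear mixed-effects model" and lists no fixed effects, so it neither includes nor excludes a baseline term. Both documents allow further exploratory modelling if the data warrant it, but specify none.

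Two other parts of the SAP bear on the point:

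- For MDASI-BT change scores, SAP 6.11.2.2 provides for "adjusting for baseline score if needed". SAP 6.11.1.2 does the same for the neurocognitive scores. The QT model has no such provision.
- SAP 5.3 describes a dynamic allocation that "will be adopted to minimize imbalance between treatment arms according to the following factors": ECOG performance status, age, and primary or secondary glioblastoma. No ECG variable is among them.

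**The concern.** A change score is negatively correlated with its own baseline, because a reading that is high by chance tends to be followed by a lower one. If one arm starts with a higher mean QT by chance, its mean delta QT will tend to be lower whatever the treatment does. A baseline covariate removes that part of the arm difference and the residual variance that goes with it.

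The terms already in the model do not do this:

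- The random patient effect describes correlation among a patient's change scores. It does not take regression to the mean out of the arm contrast.
- Delta RR accounts for the change in heart rate, not for the level at which QT started.
- The allocation method does not balance QT.

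What is at stake is the width of the between-arm 90% CIs for QT, and how far those estimates depend on the baseline draw. Protocol 10.3.2.1 calls for single ECGs, so noise in the baseline reading is not reduced by averaging replicates.

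**Working it through.** **Inputs from the documents.** The model terms and the 90% level come from SAP 6.13.6. The Protocol synopsis gives 180 patients entered, in three arms, with unequal allocation "favoring the LY2157299 plus lomustine arm" (SAP 5.2). The documents state no QT standard deviation, baseline-to-post-dose correlation, margin or power, and the numbers per arm are blacked out. There is therefore no figure of the plan's own to reproduce.

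**Assumptions.** One post-dose timepoint, 40 against 80 patients, no treatment effect, and QT = b × RR + patient effect + error, with b = 0.15. Patient-effect SD (s_b) is 12 to 18 ms and error SD (s_w) is 8 to 12 ms. RR has SD 100 ms between patients and 80 ms within patients. The RR-adjusted correlation is ρ = s_b²/(s_b² + s_w²). Each setting was simulated 4,000 times under three models: SAP terms, SAP terms plus baseline QT, and SAP terms plus baseline QT and baseline RR.

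**Formulas.**

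- With delta RR fitted, the residual variance of delta QT is 2s_w².
- Adding baseline QT multiplies the variance by 1 − s_w²/(2V), where V = b²(100² + 80²/2) + s_b² + s_w².
- Adding baseline QT and baseline RR multiplies it by (1 + ρ)/2.
- The CI width ratio is the square root of the variance ratio.

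**Numbers put in for s_b = 15, s_w = 10.** b²(10,000 + 3,200) = 0.0225 × 13,200 = 297, so V = 297 + 225 + 100 = 622. The ratio with baseline QT is 1 − 100/1,244 = 0.920. ρ = 225/325 = 0.69, so the ratio with both covariates is 1.692/2 = 0.846. The simulated ratios are slightly higher because the extra covariates use degrees of freedom.

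| s_b, s_w (ms) | ρ | Variance ratio, + QT (theory / simulated) | CI narrower | Variance ratio, + QT + RR (theory / simulated) | CI narrower |
|---|---|---|---|---|---|
| 12, 12 | 0.50 | 0.877 / 0.877 | 6.4% | 0.750 / 0.762 | 12.7% |
| 15, 10 | 0.69 | 0.920 / 0.929 | 3.6% | 0.846 / 0.865 | 7.0% |
| 18, 8 | 0.84 | 0.953 / 0.963 | 1.9% | 0.918 / 0.936 | 3.3% |

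The last column follows from √0.762 = 0.873, √0.865 = 0.930 and √0.936 = 0.967. A fourth setting (15, 10) with practically no RR variation between patients gave simulated ratios of 0.870 and 0.855, or 6.7% and 7.5% narrower.

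**In milliseconds.** The half-width under the SAP model is about 1.645 × √2 × s_w × √(1/40 + 1/80), and the last factor is 0.194. This gives about 5.4, 4.5 and 3.6 ms for the three rows. Multiplying by the width ratios for both covariates gives about 4.7, 4.2 and 3.5 ms.

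**Carry-over of imbalance.** In the three tabulated settings the SAP estimate moved by −0.23, −0.14 and −0.09 ms per ms of baseline QT difference between arms. With baseline QT added, the slope was about 0. In the middle setting the SD of baseline QT is √(0.0225 × 16,400 + 225 + 100) = √694 = 26 ms. The chance difference between arms then has SD 26 × 0.194 ≈ 5 ms. A 5 ms imbalance shifts the estimate by about 0.4 to 1.2 ms across the settings, against the direction of the imbalance.

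**Bias.** With a true difference of zero, the mean estimate lay between −0.12 and 0.03 ms for every model.

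**The case against.** The strongest reply is that this is a small efficiency preference. The arms are randomized, so the change-score contrast is unbiased and its CI already allows for chance variation in baseline. The safety set groups patients by treatment received in Cycle 1 (SAP 6.1.1), which should differ little from allocation. QTcB and QTcF outliers are summarized separately at every scheduled timepoint. All of this stands, and it limits the point to precision and conditional imbalance.

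A reader might infer more in three ways, none of which the documents support:

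- *A larger gain.* The textbook ratio (1 + ρ)/2 with the raw correlation compares a plain change score with a plain baseline-adjusted analysis. At ρ = 0.3 to 0.8 it gives 0.65 to 0.90. The SAP model already contains delta RR, so this overstates what baseline QT alone would add. The ratio applies only when both covariates are added, and then with the RR-adjusted correlation.
- *A gain in power.* Neither document states a QT hypothesis, margin or power, and the planned intervals are 90%. Any power figure would be invented.
- *A known QT signal.* Protocol 5.6.4.2 does report a Grade 3 QTc prolongation in the earlier combination study, but lists it as isolated, not serious and unrelated to study therapy. Protocol 5.6.3 finds no substantive nonclinical QT risk up to a stated concentration. The event does not make this model's precision critical.

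A fair practical objection also stands in part. SAP 6.13.6 allows a baseline ECG to be either a screening or a predose reading, yet forms delta QT from the screening reading. A covariate called only baseline QT would be ambiguous. This bears on how the fix is worded and does not remove the gain.

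**Conclusion.** The omission is real, and nothing elsewhere in either document supplies the missing term. The effect is modest. Under assumed RR-adjusted correlations of about 0.5 to 0.84, adding baseline QT narrows the between-arm 90% CI by about 2 to 6%. Adding baseline QT and baseline RR narrows it by about 3 to 13%. Adding baseline QT also removes a carry-over of about 0.09 to 0.23 ms per ms of chance baseline imbalance.

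These sizes rest on assumed SDs, an assumed QT–RR slope, a single timepoint and 40 against 80 patients, since the documents give none of these. The direction was the same in every setting examined. The current estimate is not systematically biased, and no trial decision rule depends on it. This is a free improvement.

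**What to change.** In SAP 6.13.6, add baseline QT and baseline RR as fixed covariates in the delta QT model. Both should be centred and defined as the same screening reading that is subtracted to form the delta. That wording settles which baseline is meant, including where screening readings are matched by nominal time. All other terms and the 90% CIs stay as written.

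The cost is a line of SAP text and two model degrees of freedom. No new data are needed, because the screening ECG is already collected and used. Protocol 12.2.10.1 names only the class of model, so no protocol change is needed. The covariates are best fixed in advance, so that adjustment does not become a choice made after an imbalance has been seen.
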